9.3 Specimen Banking

Subject samples collected for this study will be retained at the department of pathology and at the lab of [name] (NC7. 208). Specimens will be stored indefinitely or until they are used up. If future use is denied or withdrawn by the subject, best efforts will be made to stop any additional studies and to destroy the specimens.

As outlined in the consent form, the protocol also gives the study personnel access to patient's tumor tissue available at current or outside institutions that has been performed previously or will be done in the future. These may have been collected during prior surgery or as part of other IRB approved protocol such as the GU tissue registry study of (032011-187), PDX tissues and cancer center's tissue repository.

[name] will be responsible for reviewing and approving requests for clinical specimen from potential research collaborators outside of UTSW. Collaborators will be required to complete an agreement (a Material Transfer Agreement or recharge

agreement) that states specimens will only be released for use in disclosed research. Any data obtained from the use of clinical specimen will be the property of UTSW for publication and any licensing agreement will be strictly adhered to.

The specimens, DNA, and their derivatives may have significant therapeutic or commercial value. The Informed Consent form contains this information and informs the subject that there is the potential for financial gain by UTSW, the investigator or a collaborating researcher or entity.

The following information obtained from the subject's medical record may be provided, among other, to research collaborators when specimens are made available:

- Diagnosis
- Collection time in relation to study treatment
- Clinical outcome – if available
- Demographic data

10.0 QUALITY OF LIFE AND COST-EFFECTIVENESS

10.1 Health-Related Quality of Life (HRQOL) Analysis

The study design is to prospectively analyze the HRQOL among patients with mRCC treated with SABR and Nivolumab. While hypofractionation is hypothesized to yield greater tumor cell kill, it may also increase the normal tissue toxicity, in which case there may be a decrease in HRQOL. The primary normal tissue toxicities in patients receiving radiation depend on the location of the treatment. Prior studies have demonstrated that the most sensitive and clinically meaningful method for accurately capturing the normal tissue toxicities is via patients reported outcomes (PROs), such as HRQOL. A review of patient reported outcomes and health-related quality of life studies in the modern era of metastatic renal cell carcinoma is available highlighting the great need to assess patient reported outcomes in this patient population [81].

In this trial, we plan to assess the HR-QoL questionnaires at specific time points to minimize patient burden: baseline (pretreatment), and at subsequent follow ups. FACT-G is a measure that sums the functional well being (FWB), physical well being (PWB), the social/family well-being (S/FWB), and emotional well being (EMB). The FACT-G has been validated as well and has been used in other studies evaluating treatment options for patients with mRCC [105]. It takes about 5-10 minutes to complete and has been written at the 6th grade level. FACT has been translated into 26 languages and is available free of charge to institutions with the completion of an agreement to share data, accessible at <http://www.facit.org/translation/licensure.aspx>.

FKSI adds to the FACT-G (27 items) by including 15 items specific to kidney cancer patients. In a HRQOL study focused on patient with mRCC, a symptoms subscale questionnaire was developed and will also be administered in this study. It is 15 questions and should take less than 5 minutes to complete. This form focuses on symptoms frequently experienced by renal cell carcinoma patients and has been used in several recent mRCC studies [111]

In addition, the EQ-5D is a standardized instrument for use as a measure of health outcome. Applicable to a wide range of health conditions and treatments, it provides a simple descriptive profile and a single index value for health status. The US version of the EQ-5D will be used, to enable mapping of general HR-QoL scores from EQ-5D scores into health state utility scores (ranging from 0 to 1) for the US population. These utility scores are needed for cost-utility analysis (estimates of costs per “quality adjusted” life-year gained) [112, 113].

There is little reported on the effect on HRQOL for patients treated with Nivolumab. However, there are several detailed reports evaluating quality of life for sunitinib, sorafenib, temsirolimus, everolimus, pazopanib [114]. Thus, we propose utilizing the FACT-G, FKSI, and EQ-5D in the

patients enrolled on this study for descriptive purposes given the lack of HR-QoL data for either Nivolumab, SABR or Nivolumab+SABR in this patient population [115].

10.2 Cost-Effectiveness Analysis (CEA)

For the primary CEA analysis, we will estimate cost accumulated within 1 year after enrollment. A larger limit is possible if we have a reasonable number of people surviving at that time.

Since patients are enrolled into the study over time and some patients are still alive at the end of the study, their survival time and costs are censored. Due to censoring, we cannot use a simple average of the patients' total costs, a simple average of the patients' costs for those with complete cost information, or a Kaplan-Meier estimator on censored costs, since these all produce biased estimators of the mean costs [112]. Instead, we will use the inverse-probability weighting method to calculate average costs [113, 117]. The assumption used in this method is that censoring is independent of the survival time, or cost collection process, which is often satisfied in well-conducted clinical trials. If the new treatment can both extend patients' survival time (or quality-adjusted survival time), and save costs at the same time, the new treatment will be preferred to the current standard treatment under any willingness to pay threshold. However, if the new treatment extends survival time but costs more, cost-effectiveness analysis provides an estimate of the incremental cost of greater incremental effectiveness. For traditional cost-effectiveness analysis, treatment effectiveness is measured simply as survival time. The incremental cost-effectiveness ratio indicates the additional cost required to attain one additional year of survival. For cost-utility analysis, treatment effectiveness is measured as quality-adjusted survival time (which accounts for the impact of treatment on both mortality and morbidity, including any differences in adverse effects of treatment affecting HR-QoL). For cost-utility analysis, the incremental cost-effectiveness ratio indicates the additional cost required to attain one additional year of quality adjusted survival.

10.2.1

Projection Model and Sensitivity Analysis

If the new treatment is implemented in usual practice, some of its potential benefits to patients may extend beyond the time horizon of the clinical trial. We will explore the potential to use results from the clinical trial based cost-effectiveness analysis, augmented with information from secondary sources, to develop a model to project costs and effectiveness beyond the time horizon included in the clinical trial. Any such model projections would be subjected to probabilistic sensitivity analysis, to assess the impact of parameter uncertainty on estimated cost effectiveness results. This is typically done via Markov Modeling with probabilistic sensitivity analysis.

10.3 Quality adjusted survival time

The quality-adjusted survival time estimates need to account for the presence of censoring. Due to the induced informative censoring problem, the ordinary survival method (e.g., Kaplan-Meier estimator) cannot be applied in this case [113, 117, 118]. Accordingly, we will use the inverse-probability weighted method of Zhao and Tsiatis to carry out the survival time analysis [113, 117]. To estimate quality adjusted survival time, data from EQ-5D will first be translated into utility measures. These measures are obtained at discrete time points, so they will be interpolated into the time intervals between the visits. The quality-adjusted survival time is just an integration of the utility measures over a patient's survival time, or until the time limit similar as the cost calculation, whichever occurs earlier.

11.0 STATISTICAL CONSIDERATIONS

11.1 Study Design/Study Endpoints

This is a safety lead-in phase II clinical trial using SAbR of multiple metastatic sites concurrently administered with PD-1 blocking antibody Nivolumab for patients with metastatic clear cell renal cell cancer (RCC) who have failed at least one anti-angiogenic treatment. The primary endpoint is

RR, while the secondary endpoints include in OS, PFS, CR rate, immunologic response, toxicity and quality of life (Please see endpoint details above).

11.2 Sample Size and Accrual

The first six patients assigned will be assessed for feasibility, safety, and toxicity for interim safety of the trial 8 weeks post-registration. If more than 3 patients experience \geq Grade 3 SAE attributed to the SAbR+Nivolumab out of 6 patients, the study will be held until approval from DSMC.

The previous studies show that the maximum RR for mRCC patients treated with Nivolumab is 25%. We expect that the addition of SAbR to Nivolumab will increase the RR to 50% i.e. a 100% increase compared to the historical RR to Nivolumab alone. In our current ongoing phase II clinical trial (STU 012013-041) with similar patient population and treatment strategy of SABR + immunotherapy using IL-2, we are noticing a 53% RR with the combination whereas the historically reported response rate of IL-2 alone treatment is 20% (1). Therefore, we have increased the RR by $>150\%$. Therefore, in oncology clinical trials, it is not uncommon to see such increases since the baseline RR is often low.

The calculation of the sample size is based on the RR. In this phase II trial, we will recruit a total of 19 patients including the 6 patients that will be used for interim safety analysis. A total sample size of 19 achieves 80% power to detect 25% absolute difference in RR (25% vs. 50%) using an exact binomial test at a 0.2 two-sided significance level. To allow for potential subject dropouts, the accrual goal will be increased by an additional 2 patients for a total of 21 patients. The sample size was estimated using a sample size software PASS 14 ("Hintze, J. (2015). PASS 14. NCSS, LLC. Kaysville, Utah, USA. www.ncss.com.")

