The toxicities of Nivolumab are tolerable and well described. Given the multiple studies demonstrating excellent safety profile of SABR, including our own departmental experience, there are limited concerns for additional toxicity when they are administered sequentially [7-9]. No clinical trials combining SABR with PD-1 inhibitors are published and there is paucity of data regarding the side effect profile of the combination. However, preliminary data from our phase II trial of HD IL-2 (a form of immunotherapy with a serious toxicity profile) and SABR showed that the addition of SABR to immunotherapy did not increase toxicity (data unpublished). A phase I trial of HD IL-2 and SABR in melanoma and RCC patients has proven the safety and feasibility of this regimen [55]. In addition, we have already used SABR in five patients who are receiving Nivolumab for metastatic disease (4 with mRCC and 1 with metastatic melanoma – See table 7.3.1). Our preliminary acute toxicity data (See table 7.3.2), with a follow up ranging between 1 and 3 months, shows that the combination treatment is well tolerated with a favorable toxicity profile comparable to the published side effects of Nivolumab alone (Please see 7.2.2). Please note that the grade 4 toxicity in patient #1 was considered to be due to disease progression in the lung rather than due to the therapy itself.

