2.0 STUDY OBJECTIVES

This study is a safety lead-in phase II single institution clinical trial using Nivolumab and concurrent SABR to 1-6 metastatic sites in patients with metastatic clear cell renal cell cancer (mccRCC) who have received at least one prior anti-angiogenic therapy. Nivolumab will be dosed intravenously as per the institution guidelines, until disease progression, unacceptable toxicity or other reasons specified in the protocol. No dose modifications for Nivolumab will be allowed. SABR will be administered to 1-6 sites of metastatic disease one week after the first dose of

Nivolumab with a single (24-27 Gy) or three (11-16 Gy/fraction) fractions. The sites of larger (bulky) disease and the sites of symptomatic disease will be prioritized for treatment at the discretion of the treating radiation oncologist.

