4.0 TREATMENT PLAN

4.1 SABR Dose and Techniques

Patients should have at least 1 measurable non-CNS lesions. Lesions receiving SABR will be called “radiated” lesions. “Target” lesions will be selected from non-treated lesions. In any case, there should be at least one (non-CNS) measurable lesion for effect measurement. Prior irradiated lesions (outside of the trial) will be excluded from target lesions. SABR will be administered to 1-6 sites of metastatic disease on the 2 weeks after the second dose of Nivolumab with a single (24-27 Gy) or three (11-16 Gy/fraction) fractions. The sites of larger (bulky) disease and the sites of symptomatic disease will be prioritized for treatment.

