4.3 Duration of Therapy

Nivolumab will be dosed per standard of care approved guidelines. Nivolumab administration will be repeated, at the discretion of the treating medical oncologist until [5]:

- Disease progression as per the ir-RECIST criteria
- Inter-current illness that prevents further administration of treatment
- Unacceptable adverse event(s)
- Subject decides to withdraw from the study, **OR**
- General or specific changes in the patient's condition render the subject unacceptable for further treatment in the judgment of the principal investigator or medical oncologist.

SABR will be performed after the second Nivolumab dose but before the fourth dose (i.e. before the second Nivolumab cycles).

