5.2 Procedures During Treatment

SABR treatment requires one week for planning and one week for delivery of the 1 or 3 fractionation schemes. Thus, CT simulation and treatment planning will take place any time before the radiation. SABR will be performed after 1st cycle of Nivolumab infusion. Vital Signs, AE Assessment, Medication Review and Laboratory Review may be performed by a Nurse or Physician.

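### The six-patient safety look is timed from registration with no minimum observation after SABR, and the sections disagree on when SABR is given

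*Combined protocol and SAP*

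**What the plan says.** Section 11.2 sets the lead-in review: "The first six patients assigned will be assessed for feasibility, safety, and toxicity for interim safety of the trial 8 weeks post-registration". If more than three of the six have a Grade 3 or worse SAE attributed to the combination, the study is held until the DSMC approves. No minimum time after SABR is given there, in the stopping rule (7.8), or in the safety analysis set (6.2), which asks only for one SABR fraction and one nivolumab cycle.

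The timing of SABR is stated four times:

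- Section 2.0: "SABR will be administered to 1-6 sites of metastatic disease one week after the first dose of" nivolumab.
- Section 4.1: "on the 2 weeks after the second dose of Nivolumab".
- Section 4.3: "SABR will be performed after the second Nivolumab dose but before the fourth dose", which it glosses as "before the second Nivolumab cycles".
- Section 5.2: "SABR will be performed after 1st cycle of Nivolumab infusion".

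The nivolumab interval is left to institutional guidelines (4.2.1). The only interval quoted is three-weekly, in the account of prior trials in 1.4.2. Treatment may not start before registration (3.0), and no maximum gap between registration and dose 1 is set.

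**The concern.** The lead-in exists to judge the combination, and its event can be fully seen only after SABR has been given and followed. A clock that starts at registration guarantees no particular amount of that follow-up, and the conflicting SABR dates mean the amount cannot be read from the plan.

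This matters because 1.4.2 says "No clinical trials combining SABR with PD-1 inhibitors are published and there is paucity of data regarding the side effect profile of the combination". The site's own experience there is five patients, "with a follow up ranging between 1 and 3 months". Feasibility, safety and toxicity are the stated primary objective of this look (2.1). If it is taken too soon after SABR, the six-patient count can miss events that it was set up to catch.

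**Working it through.** **Figure in 11.2.** The only computable figure there is the sample size, and it reproduces: with 19 patients and rejection at 8 or more responses, the upper-tail error is 0.0775 and power is 0.8204. The timing point does not depend on it.

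**Do the dates agree?** Let *q* be the nivolumab interval in weeks, with dose 1 at week 0. *q* = 2, 3 and 4 are assumptions. SABR falls at week 1 under 2.0, at week *q* + 2 under 4.1, and from week *q* to week 3*q* under 4.3. Section 4.1 lies inside the 4.3 window at every *q*. Section 2.0 puts SABR before dose 2 at every *q*, so it cannot be reconciled with the other two. Section 5.2 could fit either side. Section 5.2.2 lists the first infusion cycle on Day 1, which suggests one infusion per cycle and fits 2.0. The gloss in 4.3 suggests several doses per cycle and fits the later window. A cycle is not defined.

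**Post-SABR observation at week 8** = 8 − SABR week, with no lag from registration to dose 1:

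| Source | q = 2 | q = 3 | q = 4 |
|---|---|---|---|
| 2.0 | 7 | 7 | 7 |
| 4.1 | 4 | 3 | 2 |
| 4.3 | 6 to 2 | 5 to −1 | 4 to −4 |

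A negative value means SABR has not yet been given. These are upper limits, since each week of lag removes one week. At an assumed 2-week lag, 4.1 gives 2, 1 or 0 weeks.

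**The protocol's own benchmarks.** The elective 8-week biopsy (5.1.14.2) requires more than 4 weeks after SABR. At week 8 with no lag, 2.0 meets that gap (7 weeks) and 4.1 does not at any of the three intervals. Acute adverse events (7.3.1) run to a follow-up 12 weeks after treatment. Treatment cannot precede registration, so week 8 falls inside that window whichever SABR date applies.

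**Who is affected?** Read the look as one review when patient 6 reaches week 8, using all data to that date. Even accrual of 21 patients over 5 years (Study Summary; evenness assumed) is 5 × 365.25 / 7 / 21 = 12.4 weeks per patient.

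- At 12.4 weeks per patient, patient 5 is at week 8 + 12.4 = 20.4. Even at the latest 4.3 date (20.4 − 3*q*), that leaves 14.4, 11.4 or 8.4 weeks after SABR.
- At one patient per 4 weeks (assumed), patient 5 is at week 12. That leaves 8, 7 or 6 weeks under 4.1, and 6, 3 or 0 at the latest 4.3 date.

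**Effect on the hold rule (illustration).** The rule needs at least 4 of 6. With a true risk of 0.50 per patient, the hold probability is 22/64 = 0.344. If only the sixth patient is under-observed, with half of that risk not yet visible, it is P(at least 4 of 5) + P(exactly 3 of 5) × 0.25 = 0.1875 + 0.3125 × 0.25 = 0.266.

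**The case against.** The best case for the plan is that safeguards lie outside the look. The DSMC reviews SAEs in real time and adverse events quarterly (12.5). Patients who never receive SABR are replaced (5.5.3), and 6.2 confines safety analyses to those who had both treatments. The hold sentence and 7.8 state no cut-off, so later events in the first six are not clearly excluded. Section 1.4.2 also cites a phase I trial of IL-2 with SABR and the site's phase II data without added toxicity, and expects limited additional toxicity. All of this stands and lowers the stakes, but none of it gives the lead-in decision a minimum post-SABR observation.

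A reader might go further in four ways that the documents do not support:

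- **That 2.0 is simply the mistaken section.** The one-infusion reading of a cycle makes 5.2 compatible with 2.0. If 2.0 is right, there are up to 7 weeks after SABR and most of the shortfall disappears.
- **That the biopsy gap shows early SABR was intended.** The biopsy may be done up to 2 weeks late. At week 10, 4.1 gives 10 − (*q* + 2) = 6, 5 or 4 weeks, so two- and three-weekly dosing meet the gap. No intent follows.
- **That a patient treated late in the 4.3 window always has no follow-up.** At two-weekly dosing and no lag at least 2 weeks remain. At three-weekly dosing it happens only in the last week of a six-week window.
- **That the hold rule is largely disabled.** If all six patients had half their risk unseen, the hold probability in the illustration would fall to 0.038. At the planned accrual pace the earlier patients have much longer follow-up, so that case does not fit.

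**Conclusion.** The point holds in limited form. The look has no minimum post-SABR observation, and 2.0 contradicts 4.1 and 4.3; both follow from the text without assumptions. The number of weeks available does depend on assumptions: the dosing interval, the registration-to-dose lag and which SABR date governs. At three-weekly dosing and no lag it is 7 weeks, 3 weeks, or 5 to −1 weeks.

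The likely effect on the hold decision is modest, of the order of 0.344 to 0.266 in an illustration that rests on an assumed 50% risk and a half-observed sixth patient. Faster accrual would spread the shortfall to earlier patients. It still merits correction, because little is known about the combination's toxicity and the remedy is cheap. The sample size and primary endpoint are untouched.

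**What to change.** 1. State one SABR date in 2.0, 4.1, 4.3 and 5.2, and define a nivolumab cycle.
2. In 11.2, hold the look when each of the first six patients who received SABR has completed a fixed interval after the last SABR fraction. The sponsor and the DSMC should choose the interval. The protocol's own benchmarks are more than 4 weeks (biopsy) and 12 weeks (acute adverse events).
3. Count attributed Grade 3 or worse SAEs as they occur, so that reaching four triggers the hold at once.

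**Cost.** The change is amendment wording plus some delay. With an 8-week interval, used as an example, the look for the last patient moves by the SABR week: 1 week (2.0), 5 weeks (4.1) or 3 to 9 weeks (4.3) at three-weekly dosing, and up to 12 weeks at four-weekly dosing. A three-fraction course of up to 10 days adds up to 10/7 = 1.4 weeks, and any lag to dose 1 adds its own length. The plan states no accrual pause, so with no lag the largest delay means (12 + 1.43)/12.42 = 1.1 more patients enrolled before the look at one per 12.4 weeks, or (12 + 1.43)/4 = 3.4 at one per 4 weeks. A shorter interval reduces this.

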11.3 Data Analyses Plans

Exact binomial method will be used to calculate the response rate, toxicity rate, CR rate, and the corresponding 95% confidence interval. [Exact binomial test will be used to investigate if the response rate of the treatment arm is significantly different from that of historical control.](#) PFS and OS will be estimated using the Kaplan-Meier approach along with the 95% confidence interval using Greenwood's formula. One sample log-rank tests will be conducted to investigate if OS or PFS in the treatment arm is significantly different from that of historical control.

Generalized estimating equation (GEE) analysis will be conducted to investigate if there are significant changes in surrogate makers such as CD25, CD71, CD45RO, CD107a, CD54, CD69, Ki67, ICOS/CD278 and PBMC over time. HRQoL, CEA and quality adjusted survival time analysis is described in Section 10.

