6.2 Safety/tolerability

Analyses will be performed for all subjects having received at least one fraction of SABR and one cycle of Nivolumab. The study will use the CTCAE version 4.0 for reporting of non-hematologic adverse events (<http://ctep.cancer.gov/reporting/ctc.html>) and modified criteria for hematologic adverse events.

6.3 Quality of Life (QoL)**6.3.1 Functional Assessment of Cancer Therapy-P (FACT-G) and Kidney Symptom Index (FKSI)**

Patient-reported functional status will be assessed the Functional Assessment of Cancer Therapy-General (FACT-G) (See appendix E). The FACT-G is a 28-item questionnaire that uses 5-point Likert-type response choices (0 = not at all; 1 = a little bit; 2 = somewhat; 3 = quite a bit; 4 = very much). It will take less than 10 minutes to complete the questionnaire. The Trial Outcome Indices (TOI) also will be utilized to measure the summed functional well-being, and physical well-being [102, 103]. A 5-point deterioration in the FACT-G TOI between pre-treatment and at post treatment or at year 1 will be considered clinically significant [104].

The FKSI is a 15 question validated symptom index for kidney cancer patients which has been used in several metastatic renal cell cancer studies [105]. This scale focuses on symptoms predominantly related to kidney cancer such as energy, fatigue, pain, bone pain, weight loss, shortness of breath, cough, fever, hematuria. This subscale of the FKSI-DRS was validated in another study as well [106]. The FACT-G and FKSI will

be collected prior to first Nivolumab dose (baseline), and at every subsequent follow up appointment until the patient meets primary endpoint [105][3][82].

The first analysis of change in QOL from baseline to 8 weeks will only be performed on patients who are still alive at 8 weeks. Changes in QOL will be also analyzed using all available data at baseline, 2, 4, 6, 8, 10 and 12 months with semiparametric generalized estimating equations (GEE).

Additionally, similarly we will also compare the percentage of patients with an effect size for the change in FKSI (FKSI) scores between pre-treatment and post treatment which will allow us to compare the percentage of patients whose functional status remains more similar to baseline levels.

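### Section 11.3 plans GEE tests of change in at least nine immune markers on about 19 patients without a small-sample method; run in standard form, they reject too often.

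*Combined protocol and SAP*

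**What the plan says.** Section 11.3 gives the method for the immune markers: "Generalized estimating equation (GEE) analysis will be conducted to investigate if there are significant changes in surrogate makers such as" a list of nine named items (eight markers and PBMC). The wording leaves that list open-ended. Section 6.3.1 plans to analyse QoL change at "baseline, 2, 4, 6, 8, 10 and 12 months with semiparametric generalized estimating equations (GEE"), but its GEE sentence states no significance test.

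Neither section gives a variance estimator, working correlation, reference distribution, small-sample correction or alpha for GEE.

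Section 11.2 sets the number of patients: "we will recruit a total of 19 patients including the 6 patients that will be used for interim safety analysis", and "the accrual goal will be increased by an additional 2 patients for a total of 21 patients". The only significance level in the plan belongs to the response-rate test, "using an exact binomial test at a 0.2 two-sided significance level".

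Section 2.3 lists the immune-response and biomarker work as exploratory, while 11.1 counts immunologic response among the secondary endpoints. Sections 1.6 and 10.1 describe the QoL use as descriptive.

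**The concern.** GEE inference with a robust standard error is justified as the number of independent patients grows; extra visits per patient do not substitute. With about 19 patients, two errors point the same way. The uncorrected sandwich variance is biased downward, because fitted residuals are smaller than true errors. A normal or chi-square reference also ignores the uncertainty in that variance.

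The number contributing can fall below 19. Marker draws run every 8–12 weeks until discontinuation or one year, with a further draw at one year for those who stop early (5.3, 5.4, 9.0). Section 1.4.2 cites a median PFS of 4–4.6 months on nivolumab alone.

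At stake is how many markers are reported as changed by treatment. Each false lead may be carried into the mechanistic account of the combination or into later biomarker work.

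**Working it through.** **Step 1. The plan's own figure.** Exact binomial, 19 patients, 0.10 in each tail. Reject upward at 8 or more responders: P(X ≥ 8 | 25%) = 0.0775, while the lower tail P(X ≤ 1 | 25%) = 0.0310. Power is P(X ≥ 8 | 50%) = 0.820. The stated 19 patients for 80% power reproduces. This sizing covers response rate only; none exists for the GEE tests.

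**Step 2. Inputs for the GEE check.**
- Patients K: 19 or 21 from 11.2; 15, 12 and 10 to represent attrition (assumed).
- Marker visits in year 1: 52/12 gives 4 follow-ups and 52/8 gives 6, so 5–7 visits with baseline (5.4).
- Nominal two-sided 5% (assumed).

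**Step 3. Exact size, complete data.** For Gaussian GEE with a separate mean at each visit, the uncorrected sandwich Wald statistic on q degrees of freedom is distributed as Kq/(K−q) × F(q, K−q). Hence

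true size = P[ F(q, K−q) > χ²₀.₉₅(q) × (K−q)/(Kq) ].

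At K = 19:
- q = 1: 3.841 × 18/19 = 3.639; P[F(1,18) > 3.639] = 7.25%.
- q = 4 (5 visits): 9.488 × 15/76 = 1.873; 16.8%.
- q = 5 (6 visits): 11.070 × 14/95 = 1.631; 21.6%.
- q = 6 (7 visits): 12.592 × 13/114 = 1.436; 27.4%.

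| K | single contrast | 5 df | 6 df |
|---|---|---|---|
| 21 | 7.0% | 19.5% | 24.5% |
| 19 | 7.25% | 21.6% | 27.4% |
| 15 | 7.9% | 28.0% | 36.3% |
| 12 | 8.7% | 36.5% | 47.8% |
| 10 | 9.6% | 45.7% | 59.7% |

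If the 0.2 level were carried over to these tests, the same formula at K = 19 gives 22.8% for q = 1 (1.642 × 18/19 = 1.556) and 47.9% for q = 6 (8.558 × 13/114 = 0.976).

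**Step 4. Simulated size of single contrasts and slopes, nominal 5%.** MD-t is the Mancl-DeRouen covariance with a t reference.

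| Setting | Uncorrected, z | MD-t |
|---|---|---|
| 19 patients, 6 visits, complete | 6.2–7.3% | 3.6–4.1% |
| 19 patients, 25% dropout per visit after the second | 7.0–9.0% | 3.7–4.8% |
| 12 patients, same dropout | 8.8–12.8% | 3.1–6.4% |
| 19 patients, 5–7 visits, 0–30% dropout per visit, with and without random slopes | 6.9–12.8% | 4.3–6.6% |

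The first three rows use 2,000–4,000 trials per setting (Monte Carlo error about 0.3–0.6 points), within-patient correlation 0.5 exchangeable or 0.6 AR(1), and t on K minus the number of parameters; the dropout rows include skewed outcomes. The last row uses 6,000 trials per scenario, correlation 0.6 and t on n−1. There a t-test on per-patient slopes gave 4.4–5.0%.

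**Step 5. Joint visit tests, 19 patients, complete data.** Simulation gave 21.4% (5 df) and 27.4% (6 df) uncorrected, agreeing with step 3. With W the Wald statistic under the Mancl-DeRouen covariance, referring W(K−q)/[q(K−1)] to F(q, K−q) gave 4.8% and 4.6%.

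**Step 6. Multiplicity.** For nine independent tests, the chance of at least one false positive is 1 − 0.95⁹ = 37% at a true 5%, and 1 − (1 − 0.0725)⁹ = 49% at 7.25%.

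**The case against.** The strongest reply is that the plan never chooses the uncorrected sandwich. A reader might infer from the word GEE that it does. The text supports only that no small-sample method is named, so the excess error is conditional on GEE being run in its standard form. That stands, and the conclusion is worded accordingly.

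A reader might also infer that QoL findings will be over-called. Significant change is written for the markers only; the GEE sentence in 6.3.1 states no test, and 1.6 and 10.1 call the QoL use descriptive. What remains for QoL is that uncorrected confidence intervals would be too narrow. The QoL model is itself unsettled: 6.3.1 lists seven time points in year 1, while 5.3 and 5.4 schedule questionnaires at baseline and then six-monthly. With three visits, the joint-test size at K = 19 is 9.7% (2 df).

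The upper end of the dropout range should not be read as the expected error. It needs heavy loss or far fewer than 19 contributing patients. A further set of 3,000 trials per setting gave 5.9–6.7% without dropout. It reached 13.7–15.9% only with 30% loss per visit over seven visits, which leaves 0.7⁶ = 12% of patients at the last visit. The documents state no such rate, and treatment beyond progression is allowed (2.1, 4.2.1.1).

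Nor does the correction settle everything. In that extreme setting Mancl-DeRouen with t still gave 6.7–7.5%. A t reference cannot serve a joint test over visits. Multiplicity (37% even at exact 5% tests) is the larger source of false leads. Unweighted GEE also assumes data missing completely at random, which no standard error repairs.

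**Conclusion.** The concern holds for the marker analyses in 11.3, conditional on standard GEE inference. At an assumed nominal 5% with about 19 patients, the excess is about two points for a single contrast or slope without dropout. Size rises to about 8–13% with dropout, and to about 22–27% for a joint test over 6–7 visits, a natural reading of change over time. Mancl-DeRouen with the matching t or F reference gives about 4–7%, the top of that range only for single contrasts or slopes under heavy dropout; the F result was checked on complete data only.

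These figures rest on the assumed 5% level, Gaussian or lognormal outcomes, the stated within-patient correlations and the assumed dropout patterns. The consequence is limited: the marker work is exploratory under 2.3, no stopping rule depends on it, and the response-rate test is unaffected.

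**What to change.** In 11.3, state the significance level and the form of each marker test. Then specify:
- Single contrasts or slopes: GEE with the Mancl-DeRouen bias-corrected covariance and a t reference on n−1 df, where n is the number of patients contributing; or a t-test on per-patient slopes.
- Joint tests over visits: the same covariance with the Hotelling-scaled F of step 5.
- Any QoL GEE confidence intervals in 6.3.1: the same covariance, with the analysis labelled descriptive.

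The cost is an option in the analysis code and slightly wider intervals, with no extra patients or visits. For one contrast on 19 complete patients, the standard error grows by 19/18 = 1.056 and the multiplier by 2.101/1.960 = 1.072, so intervals are about 13% wider (1.056 × 1.072 = 1.13). Multiplicity across markers and outcome-related dropout need their own statements in the plan; this change does not cover them.
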